6.3.2 Dose adjustments for QTcF prolongation

In case of QTcF >500 msec, (or QTcF prolongation >60 msec from baseline)

- 1. Assess the quality of the ECG recording and the QT value and repeat if needed
- 2. Determine serum electrolyte levels (in particular hypokalemia, hypomagnesemia). If abnormal, correct abnormalities before resuming study drug treatment.
- 3. Review concomitant medication associated with QT prolongation, including drugs with a "Known", "Possible", or "Conditional risk of Torsades de Pointes, and drugs with the potential to increase the risk of study drug exposure related QT prolongation
- 4. Check study drug dosing schedule and treatment compliance
- 5. Consider collecting a time-matched PK, and record time and date of last study drug intake.

After confirming ECG reading at site, if QTcF > 500 msec

- Interrupt study treatment
- Repeat ECG and confirm ECG diagnosis by a cardiologist
- If QTcF confirmed > 500 msec:
 - Correct electrolytes, eliminate culprit concomitant treatments, and identify and address clinical conditions that could potentially prolong the QT as per the ECG and QTc Clinical Safety Standards Guidelines Section 3.3.1.
 - Consult with a cardiologist (or qualified specialist)
 - Increase cardiac monitoring as indicated, until the QTcF returns to \leq 480 msec.
- After resolution to ≤ 480 msec, consider re-introducing treatment, and increase ECG monitoring for the next treatment(s):
 - If QTcF remains ≤ 500 msec after re-introducing treatment, continue planned ECG monitoring during subsequent treatment
 - If QTcF recurs > 500 msec after re-introducing treatment, discontinue subject from study treatment.

6.3.3 Follow-up for toxicities

6.3.3.1 Follow up for infections

Subjects should be followed closely for any signs or symptoms of infection and receive prompt appropriate treatment for any suspected infection.

6.3.3.2 Follow up on potential drug-induced liver injury (DILI) cases

DILI Diagnosis

Subjects with elevated transaminases combined with an increase in total bilirubin (TBIL) may be indicative of potentially severe DILI. These events should therefore be considered as clinically important and should be assessed appropriately to establish the cause of the abnormal liver function. The required clinical information, as detailed below, should be sought to obtain the medical diagnosis of the most likely cause of the observed laboratory abnormalities. The threshold for potential DILI may depend on the subject's baseline AST/ALT and TBIL value (Table 6-2 in Section 6.3.1); subjects meeting any of the following criteria will require further follow-up and assessments as outlined below:

- For subjects with normal ALT and AST and TBIL value at baseline: AST or ALT > 3.0 x ULN combined with TBIL > 2.0 x ULN
- For subjects with elevated AST or ALT or TBIL value at baseline: [AST or ALT > 2 x baseline] or 8 x ULN, whichever is lower combined with [TBIL > 2 x baseline AND > 2.0 x ULN]

As DILI is essentially a diagnosis of exclusion, other causes of abnormal liver tests should be considered and their role clarified before the diagnosis of DILI is confirmed.

Hepatic toxicity monitoring includes the following LFTs: albumin, ALT, AST, total bilirubin, direct and indirect bilirubin, alkaline phosphatase (fractionated if alkaline phosphatase is grade 2 or higher), creatine kinase, prothrombin time (PT) or international normalized ratio (INR) and gamma-glutamyltransferase (GGT). For subjects with Gilbert Syndrome: total and direct bilirubin must be monitored, intensified monitoring applies to changes in direct bilirubin only.

Evaluate status of liver metastasis (new or exacerbation) or vascular occlusion – CT, MRI, duplex sonography.

Perform relevant examinations (Ultrasound or MRI, ERCP) as appropriate, to rule out if LFTs are caused by cholestasis (defined as ALP elevation $> 2.0 \times ULN$ with R value < 2 in subjects without bone metastasis, or elevation of ALP liver fraction in subjects with bone metastasis).

Note: The R value is calculated by dividing the ALT by the ALP, using multiples of the ULN for both values. It denotes whether the relative pattern of ALT and/or ALP elevation is due to cholestatic ($R \le 2$), hepatocellular ($R \ge 5$), or mixed (R > 2 and < 5) liver injury.

Table 6-3 provides guidance on specific clinical and diagnostic assessments to be (OR which can be) performed locally to rule out possible alternative causes of the observed LFT abnormalities.

	in diagnostic assessments for observed LFT abnormanities
Disease	Assessment
Hepatitis A, B, C, E	IgM anti-HAV; HBsAg, IgM & IgG anti-HBc, HBV DNA; anti-HCV, HCV RNA, IgM & IgG anti-HEV, HEV RNA
CMV, HSV, EBV infection	IgM & IgG anti-CMV, IgM & IgG anti-HSV; IgM & IgG anti-EBV
Autoimmune hepatitis	ANA & ASMA titers, total IgM, IgG, IgE, IgA
Alcoholic hepatitis	Ethanol history, GT, MCV, CD-transferrin
Nonalcoholic steatohepatitis	Ultrasound or MRI
Hypoxic/ischemic hepatopathy	Medical history: acute or chronicCHF, hypotension, hypoxia, hepatic venous occlusion. Ultrasound or MRI.
Biliary tract disease	Ultrasound or MRI, ERCP as appropriate.
Wilson disease (if <40 yrs old)	Caeruloplasmin
Hemochromatosis	Ferritin, transferrin
Alpha-1-antitrypsin deficiency	Alpha-1-antitrypsin

Table 6-3Clinical and diagnostic assessments for observed LFT abnormalities

Other causes should also be considered based upon subject's medical history (Hyperthyroidism / thyrotoxic hepatitis – T3, T4, TSH; CVD / Ischemic hepatitis – ECG, prior hypotensive episodes; T1D / glycogenic hepatitis).

Following appropriate causality assessments, as outlined above, the causality of the drug is estimated as "probable" i.e. >50% likely, if it appears greater than all other possible causes of liver injury combined. The term "drug-induced" indicates *probably caused* by the drug, not by something else, and only such a case can be considered a DILI case and should be reported as an SAE.

DILI Management

In the absence of cholestasis, these subjects should be immediately discontinued from study drug treatment, and repeat LFT testing as soon as possible, preferably within 48 hours from the awareness of the abnormal results. The evaluation should include laboratory tests, detailed history, physical assessment and the possibility of liver metastasis or new liver lesions, obstructions/compressions, etc.

- 1. Laboratory tests should include ALT, AST, albumin, creatine kinase, total bilirubin, direct and indirect bilirubin, GGT, prothrombin time (PT)/INR and alkaline phosphatase.
- 2. A detailed history, including relevant information, such as review of ethanol, concomitant medications, herbal remedies, supplement consumption, history of any pre-existing liver conditions or risk factors, should be collected.
- 3. Further testing for acute hepatitis A, B, C or E infection and liver imaging (e.g. biliary tract) may be warranted.
- 4. Obtain PK sample, as close as possible to last dose of study drug to determine exposure to study drug if PK analysis is performed in the study.
- 5. Additional testing for other hepatotropic viral infection (CMV, EBV or HSV), autoimmune hepatitis or liver biopsy may be considered as clinically indicated or after consultation with specialist/hepatologist.

All cases of DILI confirmed on repeat testing meeting the laboratory criteria defined above, with no other alternative cause for LFT abnormalities identified should be considered as "medically significant", thus, met the definition of SAE (Section 8.2.1) and must be reported as SAE using the term "potential drug-induced liver injury". All events must be followed up with the outcome clearly documented. Results of tests as well as other clinically important information will be recorded in the eCRF.

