Discontinuation from study treatment	Point/time when the subject permanently stops receiving the study treatment for any reason (prior to the planned completion of study drug administration, if any). Subject agrees to the other protocol required assessments including follow-up. No specific request is made to stop the use of their samples or data.
Dosage	Dose of the study treatment given to the subject in a time unit (e.g. 200 mg every 21 days)
Electronic Data Capture (EDC)	Electronic data capture (EDC) is the electronic acquisition of clinical study data using data collection systems, such as Web-based applications, interactive voice response systems and clinical laboratory interfaces. EDC includes the use of Electronic Case Report Forms (eCRFs) which are used to capture data transcribed from source data/documents used at the point of care.
Enrollment	Point/time of subject entry into the study; at which informed consent must be obtained. The action of enrolling one or more subjects
Investigational drug/ treatment	Drug whose properties are being tested in the study.
Medication number	A unique identifier on the label of medication kits
Other treatment	Treatment that may be needed/allowed during the conduct of the study (i.e. concomitant or rescue therapy)
Subject Number (Subject No. NOVDD) Subject Number (Subject No. NCDS)	A unique identifying number assigned to each subject/subject/healthy volunteer who enrolls in the study
Patient-Reported Outcome (PRO)	A measurement based on a report that comes directly from the patient about the status of a subject's health condition without amendment or interpretation of the patient's report by a clinician or anyone else
Period	The subdivisions of the trial design (e.g. Screening, Treatment, Follow-up) which are described in the Protocol. Periods define the study phases and will be used in clinical trial database setup and eventually in analysis
Perpetrator drug	Is the drug which affects the pharmacokinetics of the other drug
Personal Data	Subject information collected by the Investigator that is coded and transferred to Novartis for the purpose of the clinical trial. This data includes subject identifier information, study information and biological samples.
Randomization	The process of assigning trial subjects to investigational drug or control/comparator drug using an element of chance to determine the
	assignments in order to reduce bias.

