	Permanently discontinue study treatment.
Concomitant elevations of AST or ALT and total bilir	ubin ^c
With normal baseline LFTs:	Interrupt study treatment. Assess if case is true DILI
Grade 2 ALT/AST (>3.0 x ULN) with bilirubin > 2.0 x ULN without evidence of cholestasis ^d (unless Gilbert's syndrome)	(Note: If total bilirubin > 3.0 x ULN is due to the indirect (non-conjugated) component only, and hemolysis as the etiology has been ruled out as per institutional guidelines (e.g., review of peripheral blood smear and haptoglobin determination), continue treatment at the discretion of the investigator.)
	If DILI confirmed - Permanently discontinue
	If Not DILI – interrupt treatment. Treat the identified cause according to institutional guidelines. Repeat LFTs within 48-72 hours, then monitor weekly, till enzyme levels resolve to ≤Grade 1 or Baseline.

-			
Co	ofida	entia	L
1,0		- III AI	

Dose Schedule modifications for Canakinumab ^a	
Worst toxicity	
CTCAE Version 5.0 during a cycle of therapy	
	Note: For additional information on follow-up of potential drug induced liver injury cases, refer to Section 6.3.3.2.
With abnormal baseline LFTs: ALT or AST >2 x baseline OR ALT or AST >8 x ULN (whichever is lower) combined with total bilirubin >2.0x ULN	After recovery, re-administration of study treatment could be considered only if Investigator assesses benefit to outweigh the risk. Note: For additional information on follow-up of potential drug induced liver injury cases, refer to Section 6.3.3.2.
Investigation (metabolic)	
Asymptomatic amylase and/or lipase elevation	
Grade 1 (> ULN - 1.5 x ULN)	May maintain dose level
Grade 2 (> 1.5 - 2.0 x ULN; > 2.0 -5.0 X ULN and asymptomatic)	May maintain dose level
Grade 3* (> 2.0 - 5.0 x ULN with signs or symptoms; > 5.0 ULN and asymptomatic)	Recommendation: Omit dose : If resolved to grade ≤ 1 or baseline in ≤ 7 days, then maintain dose level If resolved to grade ≤ 1 or baseline in > 7 days, then discontinue subject from study medication (mandatory)
Grade 4* (> 5.0 x ULN and with signs or symptoms)	Mandatory: Discontinue subject from study drug treatment.
*Note: A CT scan or other imaging study to assess the pa amylase and/or lipase. If asymptomatic Grade 2 elevation from study treatment.	ncreas, liver, and gallbladder must be performed within 2 weeks of the first occurrence of any ≥ Grade 3 of s of lipase and/or amylase occur again after restarting therapy, subjects will be discontinued permanently

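### For suspected drug-induced liver injury (DILI) with normal baseline liver tests and no cholestasis, Protocol 6.3.3.2 orders discontinuation before DILI is confirmed or excluded, while Table 6-2 orders interruption and a permanent stop only on confirmation

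*Protocol*

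**What the plan says.** Two current parts of the protocol cover the same liver finding.

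- **Table 6-2 (Section 6.3.1), concomitant elevations, normal baseline.** The trigger is "Grade 2 ALT/AST (>3.0 x ULN) with bilirubin > 2.0 x ULN without evidence of" cholestasis, with an exception for Gilbert's syndrome. The first action is "Interrupt study treatment. Assess if case is true DILI". Two branches follow: "If DILI confirmed - Permanently discontinue", or "If Not DILI – interrupt treatment. Treat the identified cause according to institutional guidelines". The same part of the table also states: "After recovery, re-administration of study treatment could be considered only if Investigator assesses benefit to outweigh the risk". In the extracted text it is unclear which row this last cell belongs to. The table refers the reader to 6.3.3.2 for further information on follow-up.
- **Section 6.3.3.2.** For subjects with normal ALT, AST and bilirubin at baseline the criterion is "AST or ALT > 3.0 x ULN combined with TBIL > 2.0 x ULN". Under DILI Management, when cholestasis is absent, "these subjects should be immediately discontinued from study drug treatment", with liver tests repeated preferably within 48 hours. The evaluation for other causes is described after that.
- **Glossary of terms.** Discontinuation from study treatment is the "Point/time when the subject permanently stops receiving the study treatment for any reason (prior to the planned completion of study drug administration, if any"). The separate entry for study treatment discontinuation is likewise permanent.
- **Sections 6.3.1 and 7.1.4.** Section 6.3.1 places mandatory permanent discontinuation in Table 6-2 or in the Section 7.1.4 list. Section 7.1.4 refers back to Table 6-2 and adds its own list, which does not name suspected DILI.

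**The concern.** A site facing this finding must act within hours. The table tells it to hold drug and find out; the follow-up section tells it to discontinue and then find out. With the glossary definition applied, the second instruction permanently ends treatment for a subject whose abnormality may turn out to have another cause, such as a biliary obstruction or viral hepatitis. The first leaves that subject on hold while the cause is treated.

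What is at stake is consistent handling of a liver-safety event across sites, and with it the exposure and discontinuation summaries. No sample size, alpha or power figure is involved.

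**Working it through.** No arithmetic applies. The check is whether the two texts really address the same subject at the same moment, and whether they can be read as saying the same thing.

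1. **Same subject?** Both use ALT or AST above 3x ULN with bilirubin above 2x ULN in subjects with normal baseline values, and both limit the instruction to cases without cholestasis. Apart from the Gilbert's exception written into the table, the trigger is the same.

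2. **Same moment?** Could the subjects in the 6.3.3.2 sentence be confirmed cases only? The paragraph just before it does say what counts as a DILI case. Three things rule that reading out. The sentence itself orders repeat testing, timed from awareness of the abnormal results. The DILI Diagnosis text requires alternative causes to be clarified before DILI is confirmed, and the search for them comes after the sentence. Confirmation on repeat testing with no other cause found appears only at the end of the section, where SAE reporting is set out. So the sentence acts on suspected cases, as the first line of the table cell does.

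3. **Same action?** Compare by eventual diagnosis:

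| Situation | Table 6-2 | Section 6.3.3.2 with glossary |
|---|---|---|
| At detection | Interrupt | Discontinue (permanent) |
| DILI confirmed | Permanent stop | Permanent stop |
| DILI excluded | Interruption while the cause is treated | Already permanently stopped |

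The first row differs in status but not in immediate dosing: drug is withheld either way. The second row agrees. Only the third row gives a different result for the subject.

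4. **Which text governs?** Sections 6.3.1 and 7.1.4 both send the reader to Table 6-2 for mandatory discontinuation. Section 6.3.3.2 sits under follow-up for toxicities and is not named as a source of such rules. The structure favours the table, although no sentence says that it overrides 6.3.3.2.

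5. **Does it reach the analysis?** SAP 2.5.1 handles discontinuation of study treatment by treatment policy, so DFS assessments count whichever instruction a site follows. SAE reporting of DILI under 6.3.3.2 depends on confirmation without another cause, not on whether drug was held or stopped.

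6. **Abnormal baseline.** Here the comparison cannot be completed. The table row is broken in the extracted text, so its action cell cannot be assigned with confidence. The criteria also differ: Table 6-2 asks for bilirubin above 2x ULN, while 6.3.3.2 asks for bilirubin above both 2x baseline and 2x ULN. The demonstrated conflict is therefore the normal-baseline one.

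**The case against.** The best defence is that the protocol already shows which text governs dosing, so this is one loose sentence in a follow-up section rather than two competing rules. That largely stands, and it settles the direction of the fix. It does not remove the conflict, because the table row itself sends the site to 6.3.3.2, where the contrary order is found.

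A second argument is that the 6.3.3.2 sentence never says permanently, and that the protocol's usage is not uniform. Footnote c to Table 6-2, on combined elevations below the thresholds, speaks of discontinuing treatment and then of restarting after resolution. This has some force: a site could read the sentence as a hold. But both glossary entries say permanent, and for this very finding the table separates interruption from discontinuation. The permanent reading therefore rests on the glossary, and is stated here on that basis.

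Third, part of the evaluation does come first, since cholestasis has to be excluded before the sentence applies. That is correct. The order precedes confirmation or exclusion of DILI, not all work-up.

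A reader might go further in three ways that the documents do not support:

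- **A total of doses lost.** This would need the number of such cases, the share in whom DILI is excluded, recovery within the 42-day limit of 6.3.1, and a decision to restart. None is given, and the row to which the restart cell belongs is unclear.
- **An end-of-treatment visit that cuts the work-up short.** Section 7.1.4 asks for the visit within 7 days or as soon as it can be arranged. Section 7.1.6.1 requires follow-up to resolution or stabilisation when treatment is stopped for an adverse event.
- **Bias in the primary result.** Treatment discontinuation does not censor DFS.

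**Conclusion.** The point holds for subjects with normal baseline liver tests and non-cholestatic concomitant elevation. Section 6.3.3.2 tells the site to discontinue before DILI is confirmed or excluded; Table 6-2 tells it to interrupt and to stop permanently only on confirmation. Table 6-2 is the text that the rest of the protocol points to, so the 6.3.3.2 sentence is out of line.

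The size is small. The result differs only for subjects in whom DILI is then excluded; no count is given and they are probably few. The 6.3.3.2 wording errs on the cautious side. Primary DFS and DILI SAE reporting are not touched. The conclusion assumes that the glossary meaning of discontinuation applies to the sentence. It is a minor correction, still worth making because a liver-safety instruction should have one meaning.

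**What to change.** Leave Table 6-2 unchanged. Replace the 6.3.3.2 sentence with wording to this effect: *If cholestasis is absent, interrupt study treatment immediately, repeat the liver tests without delay (within 48 hours if possible), and discontinue treatment permanently if DILI is confirmed, as per Table 6-2.* This keeps both the immediate hold and the mandatory stop for confirmed DILI.

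The existing sentence also covers abnormal-baseline subjects. Before applying the new wording to them, the sponsor should check the intended action in the original table row.

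The cost is one sentence and a communication to sites. Data collection and the SAP do not change.

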6.4 Concomitant medications

The investigator should instruct the subject to notify the study site about any new medications he/she takes after signing the informed consent. All medications including supplements and herbal/natural medications, surgeries, and significant non-drug therapies (including physical therapy and blood transfusions) taken within 30 days of screening and administered after the subject has signed informed consent must be listed on the appropriate eCRF.

For any antineoplastic therapy, surgery, or radiotherapy initiated after the start of study treatment, the reason for its use must be clearly documented and cancer recurrence must be assessed and documented.

Prior treatment for TB infection should be listed on the eCRF. Influenza vaccines administered two years prior to study start and pneumococcal vaccines administered five years prior to study start should be recorded on the eCRF. Vaccinations taken during the trial should also be reported on the eCRF. Subjects must be discontinued from the trial if administered any live and attenuated vaccines during the course of the study (see Section 6.4.2).

Confidential

Subjects who are on warfarin or warfarin like treatment with narrow therapeutic index should have their international normalized ratio (INR) measured locally and warfarin or warfarin like treatment dose adjusted accordingly within one month from starting study treatment. This is a general precautionary measure because canakinumab is not expected to interact with warfarin.

Drug-drug interaction potential

No formal drug-drug interaction studies have been conducted with canakinumab. Elimination pathways for IgG type monoclonal antibodies such as canakinumab are distinct from metabolic pathways of small molecules. The IgG-based molecules are cleared from the body by a combination of processes such as proteolysis by the liver, elimination by the Reticuloendothelial System and nonspecific endocytosis, whereas small molecular weight drugs are typically eliminated through CYP450-mediated oxidation pathways and are therefore not expected to affect the pharmacokinetics of canakinumab. The expression of hepatic CYP450 enzymes may be suppressed by the cytokines that stimulate chronic inflammation, such as IL-1 β . Thus, CYP450 expression may be normalized when potent cytokine inhibitory therapy, such as canakinumab is introduced.

6.4.1 Permitted concomitant therapy

Potential drug interactions between study drug and concomitant medications should always be taken into consideration.

6.4.2 **Prohibited concomitant therapy**

6.4.2.1 Immunosuppressants

Use of any treatments below is NOT allowed after the start of study treatment due to potential increase in immunosuppressant related concomitant conditions. They are prohibited for the duration of the study and for at least 130 days after discontinuation of study treatment.

If a subject chooses to continue one of the medications below, they would still be required to be followed as per protocol to assess for NSCLC disease recurrence.

- Any anti retro-virals and / or any biologic drugs targeting the immune system (e.g., TNFα blockers, anakinra, rituximab, abatacept, tocilizumab)
- immune modulating agent in doses with systemic effects e.g.:
 - i. Prednisone >20 mg (or equivalent) oral or intravenous daily for >14 days;
 - ii. Prednisone > 5 mg and \leq 20 mg (or equivalent) daily for > 30 days;
 - iii. Equivalent dose of methotrexate >15 mg weekly.
- Live or attenuated vaccines within 90 days of study treatment and after initiation of study drug. Subjects must be discontinued from the trial if administered any live or attenuated vaccine during the course of the study.

